3.1.3 Justification for Part B Design

In animal experiments, no saturation of the sstr2 was observed when higher peptide mass doses were administered in a xenograft mouse model.[39] Nevertheless, the effect of the increasing peptide mass dose and the peptide mass at which lesion receptor saturation occurs in humans is unknown. The extrapolation from animal experiments may be limited by the fact that, in these

xenografts, receptor density was relatively high in comparison to normal distribution of receptors in the mouse.

Receptor saturation by the peptide is predicated on:

- (a) the number of receptors in nontumoural tissue (physiological expression) and
- (b) tumour burden and related sstr2 density (total receptor burden).

Regardless of tumour type, the higher the receptor burden the more peptide maybe required before saturation occurs. It is therefore important that the peptide masses being studied in this protocol are evaluated for sstr2 saturation. Hence Cohorts 3 and 6 will evaluate the peptide mass and specifically if receptor saturation has occurred, starting with 300 µg for Cycle 1, then increasing to 700 µg and 1300 µg respectively for Cycle 2 before repeating the 300 µg dosing for Cycle 3 (see [Figure 13](#)). Thus, the tumour-to-background dose ratio, and the tumour-to-bone-marrow dose ratio, using imaging dosimetry, can be evaluated in the same subjects. In these cohorts, administering 4.5 GBq/cycle, which was shown to be tolerated in Part A of the study, will allow comparison of intra-subject variability of the uptake due only to the peptide mass. It also allows Cohort 3 to start in parallel to Cohort 1 which is the next logical increase in dosing at 300 µg (6 GBq per cycle) following Part A.

The other cohorts in Part B will be initiated in a staggered manner after gaining experience with previous cohorts, thereby allowing safer investigation at higher radioactivity and/or higher peptide mass dose. If tumour sstr2 saturation is observed, then the lower peptide dose will be confirmed. Therefore, Cohorts 7 and 8 will be cancelled if the peptide saturation is seen in Cohorts 3 and/or 6. Similarly, Cohort 2 may be cancelled if a peptide mass dose range of 700 µg to 1300 µg is found to be optimal.

Subject numbers

Cohorts 3 and 6 will require 8 subjects to ensure there is sufficient power to demonstrate any tumour sstr2 saturation. Therefore 10 subjects will be enrolled to obtain a minimum of 8 completed subjects. All remaining cohorts (1, 2, 4, 5, 7 and 8) will enrol three to five subjects to obtain a minimum of three completed subjects per cohort.

Hence, it is anticipated that 10 subjects will be enrolled in Cohorts 3 and 6, and five subjects will be enrolled in Cohort 1, so the end-point can be achieved in these initial three cohorts rapidly (total of 25). To maintain the subject numbers to a maximum of 40 in Part B, if all remaining cohorts are utilised (total of five), each will have three subjects enrolled (total of 15).

Change in eligibility criteria for Part B

To ensure sufficient precision for the imaging dosimetry (specifically in Cohorts 3 and 6, but also for the whole study), eligibility will require a minimum of two lesions ≥ 20 mm in diameter. Tumour dosimetry should be performed on tumour lesions identified by the imaging core laboratory and on no more than five lesions (maximum two per organ, size ≥ 20 mm diameter, accessible for dosimetry). Furthermore, this ensures the modelling is based on a minimal total receptor burden.

Infusion rate

The i.v. infusion of ^{177}Lu -OPS201, should be at a rate of 10 mL/h over 120 minutes (see Section 6.2.1).

Investigators are advised that prophylaxis may be considered if the patient is thought to be at increased risk of infusion-related reactions as per the site's standard of care (see also 6.3.3 and Section 6.3.4). Appropriate treatment should be administered should an infusion-related reaction occur including somatostatin analogues. The administered radioactivity and mass dose follows the escalation scheme (see Section 6.2).

3.1.4 Long-Term Follow-Up

The long-term follow-up period will start after the EOCT/end of additional cycles (EOAC)/early withdrawal (EW) Visit.

Tumour assessments will be performed every 3 months (± 2 weeks) until whichever occurs first: documented disease progression (radiological or clinical as per the investigator's judgment), 2 years after the EOCT/EOAC/EW Visit, withdrawal of consent, lost to follow-up or death.

Safety assessments, and the subject's status, will be performed every 3 months (± 2 weeks) until whichever occurs first: 2 years after the EOCT/EOAC/EW Visit, withdrawal of consent, lost to follow-up or death; please refer to Section 8.1.4.1.

After the long-term follow-up period is completed i.e. 2 years after the EOCT/EOAC/EW Visit, all subjects will be invited to participate in a safety surveillance study, as part of a separate study protocol. All subjects will be asked to sign a new informed consent form to enter this study. The purpose of the safety surveillance study is to monitor any long-term effects of ^{177}Lu -OPS201 up to 5 years from the first dose of ^{177}Lu -OPS201.

The schedule of assessments is provided in a flow chart (see Section 5.1) and is listed in Section 5.2. Unless otherwise specified, all assessments will be performed by the investigator or accredited study personnel.

Extra visits, examinations, tests and interventions can be performed at any time if clinically indicated, as judged by the investigator.

3.1.5 Additional Optional Cycles, Part B

If a subject tolerates the treatment well and shows clinical benefit (e.g. CR, PR, or SD) up to two additional cycles at a radioactivity dose adjusted based on dosimetry results can be administered to this subject provided limiting organ absorbed dose levels have not been exceeded. Two cycles would consist of ^{177}Lu -OPS201 administration every 8 weeks ($+2$ weeks, or plus up to 4 weeks in case of AEs which are not adequately recovered) with administration of the same peptide mass dose as Cycle 1. In this case, subjects will have the same assessments as during the core treatment cycles and up to EOAC or EW except for exploratory biomarkers **CCI**. Dosimetry will thus be performed after each additional cycle to prevent exceeding limiting organ absorbed doses. For these subjects, an EOAC visit will be done 8 weeks (± 5 days) after the last ^{177}Lu -OPS201 dose administration. In this case, the 2-year long-term follow-up will start at the EOAC (instead of EOCT).

The decision to administer additional cycles or any other antitumoural treatment is at the investigator's and subject's discretions and must be discussed with and confirmed by the sponsor. However, the investigator should follow the following rules before proceeding to any additional administration:

- subjects with DLTs after first, second or third administration will be discontinued from ^{177}Lu -OPS201.
- subject will be eligible for an additional administration of ^{177}Lu -OPS201 only if:
 - renal function and blood cell counts are in the range defined in the study inclusion criteria (#12 and #13), within the treatment cycle.
 - organ absorbed doses did not exceed 1.5 Gy in bone marrow (BM) and 23 Gy in kidneys.
 - subject is likely to benefit from additional cycles of ^{177}Lu -OPS201 therapy.

The planned maintenance dose for any cycle may be adjusted such that the limiting organ absorbed doses are not exceeded.

Subjects who are to receive additional cycles of therapy will undergo the EOCT assessment

after Cycle 3. Where possible, the EOCT visit and Visit 4, Day 1 of the first additional cycle can be combined. An additional EOAC assessment will be done 8 weeks after the last dose of therapy.

3.2 Primary and Secondary Endpoints and Evaluations

3.2.1 Primary Safety Endpoints and Evaluations

Frequencies and/or descriptive summaries of standard safety and tolerability parameters: AEs (including SAEs) according to National Cancer Institute (NCI) Common Terminology Criteria for Adverse Events (CTCAE) v5.0 and vital signs, laboratory tests (haematology, biochemistry and urinalysis, and pituitary markers), 12-lead and Holter electrocardiogram (ECG), DLTs, physical examination results and use of concomitant medication throughout the study.

3.2.2 Secondary Endpoints and Evaluations

3.2.2.1 Biodistribution and Radioactive Pharmacokinetics of the Radiopharmaceutical Endpoints

- Maximal uptake (%) at the target lesions;
- Maximal uptake (%) in discernible organs and blood;
- AUC of ^{177}Lu -OPS201 in discernible thoracic and abdominal organs, target lesions and blood;
- Terminal half-life of radioactivity concentrations of the radiopharmaceutical in blood.

3.2.2.2 Radiation Dosimetry Endpoints

- Organs receiving the highest absorbed dose;
- Specific absorbed dose to the target lesion (Gy/GBq);
- Specific absorbed dose per organ (Gy/GBq);
- Cumulative absorbed organ doses (Gy).

3.2.2.3 OPS201 Pharmacokinetics Endpoints

- If OPS201 levels are measurable in plasma and urine, PK parameters of OPS201 (including, but not limited to, maximum observed concentration (C_{\max}), AUC, elimination half-life ($t_{1/2}$), apparent total body clearance of the drug from plasma (CL), apparent volume of distribution (Vd), cumulative amount of unchanged drug excreted into the urine (Ae), renal clearance of the drug from plasma (CL_R) will be derived using the noncompartmental approach on the individual plasma concentration-time profiles of OPS201 and on the individual urine concentrations.

CCI

3.2.2.4 Secondary Efficacy Endpoints

- Objective tumour response based on RECIST v1.1 (CT/MRI scan) by calculating best overall response (BOR), overall response rate (ORR) and disease control rate (DCR);
- PFS based on RECIST v1.1.

3.2.2.5 Influence of ^{177}Lu -OPS201 PRRT on the Quality of Life of the Subjects

- Quality of Life Questionnaire ((QLQ)-C30; GI.NET21) change from baseline to EOCT.

3.3 Exploratory Endpoints

CCI

3.4 Randomisation and Blinding

This is a nonrandomised, open label study. All eligible subjects will be assigned active study medication according to the radioactivity/peptide mass dose escalation plan. Independent readers will evaluate SPECT/CT Imaging and will be blinded to the radioactivity and peptide mass dose, investigator site and clinical status of the subject, including pathology, laboratory, medical history and physical examination findings.

Independent readers are specialised radiologists and/or nuclear medicine physicians who are experienced in reading SPECT/CT scans. To minimise inter- and intra-reader variability in results, the readers will be specifically trained for this protocol. See the Imaging Review Charter.

3.5 Maintenance of Randomisation and Blinding

This is a nonrandomised, open-label study.

3.6 Study Treatments and Dosage

The study treatment is manufactured and supplied to the clinical site as follows:

- clinical sites located in North America: from a central contract manufacturing organisation (Sofie Co., dba Sofie, [name]);

- clinical sites located in Europe: from a local radiopharmacy or from a central contract manufacturing organisation (Sofie Co., dba Sofie, [name]);
- clinical sites located in Australia: from a local radiopharmacy or from a central radiopharmacy (Brett and Peter Pty Ltd, located at Australian Radiopharmacy Group, [name]).

The study treatment will be supplied in a type 1 borosilicate glass vial sealed with a chlorobutyl stopper and aluminium seal, within a secondary shielding container, and is shipped inside Type A package for transporting radioactive materials when relevant. The study treatment will be labelled according to good manufacturing practice (GMP) and any applicable local laws/regulations.

The investigator's representative will receive:

- a Certificate of Analysis for each treatment which reflect the product release statement;
- Material Data Safety Sheet;
- packaging order.

Each label will be designed in accordance with Appendix 13 of the European Union (EU)-GMP and in accordance with specific local requirements if any.

For Part A the study treatment is a 20 mL solution for injection with OPS201 peptide mass dose of 300 µg with applied radioactivity of 4.5 GBq ¹⁷⁷Lu-OPS201 at the intended time and date of administration.

For Part B, the study treatment is a ready-to-inject 20 mL solution with OPS201 peptide mass dose nominally of either 300, 700 or 1300 µg and applied radioactivity dose of 4.5 GBq to 7.4 GBq ¹⁷⁷Lu-OPS201 at the intended time and date of administration.

The investigator or designee will only dispense the study treatment to subjects included in this study. Each subject will be given the study treatment carrying his/her number.

A more detailed description of administration procedures is given in Section 6.2.

3.7 Study Duration

The estimated core trial duration of Part A is 18 to 21 months (for all subjects) including 6 to 10 months of treatment for a single subject, while the long-term follow-up will last for up to 2 years after the EOCT/EW Visit. The estimated core trial duration of Part B is 14 to 20 months (for all subjects) including 6 to 10 months of treatment for a single subject, while the long-term follow-up will last for up to 2 years after the EOCT/EOAC/EW Visit. After the long-term follow-up period is completed i.e. 2 years after the EOCT/EOAC/EW Visit, all subjects will be invited to participate in a safety surveillance study (see Section 3.1.4).

3.8 Safety Review Committee (Part A) and Data Review Board (Part B)

The SRC will be composed of all investigators, who have treated at least one subject in the respective cohort with study medication, a dosimetry expert evaluating the dosimetry data of the study, an independent haematology expert and at least one sponsor representative. A specific charter will be developed to define roles and responsibilities, as well as the data set to be reviewed by the SRC.

This study will be performed in two phases:

Part A (15 subjects)

Initially, six subjects will be treated in Part A. Each subject will receive three cycles of 4.5 GBq (target radioactivity of 4.5 GBq±10%) ¹⁷⁷Lu-OPS201 (target dose of 300±50 µg), 8 weeks apart (+2 weeks or up to +4 weeks in case of AEs which have not adequately recovered).

An SRC meeting will be held before exposing the remaining nine subjects in Part A to the entire number of planned administrations. Safety and dosimetry data from the first six subjects (data obtained up to 8 weeks after the last administration for each subject) will be evaluated during this SRC.

Dose limiting toxicity definition: IRPP related AEs with a severity of Grade 3 or higher are considered DLT, with the exception of hair loss, lymphopenia, nonfebrile neutropenia lasting <4 weeks and thrombocytopenia lasting <4 weeks.

- If DLTs occur in $\leq 33\%$ of subjects, the remaining nine subjects will continue at the same radioactivity level.
- If DLTs occur in $> 33\%$ of subjects, the administered radioactivity will be reduced to a cumulative radioactivity which did not lead to DLT occurrence with this frequency, e.g. the number of administrations will be reduced from three to two.

After treatment completion of the sixth subject (Part A), the SRC will decide, based on the safety and dosimetry data from Part A, if a radioactivity escalation is applicable in Part B.

The decision must be unanimous among the SRC members. The IRB/ECs will be notified of the radioactivity dose decision by the SRC.

Part B (up to 40 subjects)

The DRB will consist of a team of “permanent” decision makers (the core team), including selected principal investigators and Ipsen personnel. All final decisions will be made by the core team. The number of DRB meetings may change as needed and the DRB can be called upon rapidly if there is a safety issue of concern in a cohort. The aim is to have all meetings via conference call, but if the timing does not allow for this, then the meeting can be conducted via email exchange or two conference calls with split attendees. A DRB charter will be developed with further details. Ad hoc DRBs can be convened at any time during the trial. See [Appendix 3](#) for the details of the review required by the DRB.

Dose escalation (peptide mass dose and radioactivity, see [Figure 13](#)) will primarily be decided based on the clinical and safety data of the subjects.

Dose limiting toxicity (DLT) definition in Part B: IRPP related AEs with a severity of Grade 3 or higher are considered DLTs, with the exception of hair loss, lymphopenia, nonfebrile neutropenia lasting <4 weeks and thrombocytopenia lasting <4 weeks.

Proceeding to the next cohort will be determined by the following DLT rules based on three evaluable subjects:

If DLTs occur in $> 33\%$ of subjects in the cohort, the next cohort will not be initiated.

- If DLTs occur in $\leq 33\%$ and ≥ 2 of the three subjects have a cumulative absorbed dose in each target organ exceeding the acceptability limits (1.5 Gy in BM and 23 Gy in kidney), subjects in the next cohort will receive the same cumulative radioactivity or less than in the preceding cohort.
- If DLTs occur in $\leq 33\%$, and < 2 of the three subjects did not reach the cumulative absorbed dose in each target organ (1.5 Gy in BM and 23 Gy in kidney), the next cohort will be initiated as planned.

Each dose escalation (both peptide mass and radioactivity) will be carefully evaluated by the DRB. As safety and dosimetry information becomes available in other cohorts, this data will be used to evaluate the on-going cohorts and the subjects’ dosing within the cohorts.

The DRB can make a recommendation as to the radioactivity dosing for the next cohort. This could include continuing the current cohort to complete five subjects for review. Alternatively, if any cohort dose (peptide or radioactivity) is closed down, with agreement from the DRB, the

next lowest dose may have three more subjects entered to confirm this is the maximum tolerated dose.

Based on the overall safety results, the DRB can also decide to start earlier or delay cohorts depending on the information available. Notification will be given to the principal investigators if this is to occur, with the rationale, as well as to the IRB/EC.

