After the three core-treatment cycles, up to two additional cycles of ^{177}Lu -OPS201 can be administered if the subject continues to meet the criteria outlined in [Section 6.4.2](#) and the subject has clinical benefit (defined as CR, PR or SD). The additional cycles are optional and must be discussed with the sponsor before administration.

The population of Cohorts 3 and 6 will enrol eight to 10 subjects to ensure a minimum of eight completed subjects. All remaining Cohorts (1, 2, 4, 5, 7 and 8) will enrol three to five subjects to ensure a minimum of three completed subjects per cohort. A completed subject is defined as one who has received at least 3 cycles of study treatment or fewer than 3 cycles if one of the following has occurred: exceedance of organ dose limits, treatment-related safety issues or disease progression.

Figure 2 Study Design - Part B

DRB=data review board; GBq=gigaBecquerel; SRC=safety review committee.

Priority for the conduct of the cohorts is as follows: Cohorts 1 and 3, Cohort 6, Cohort 4, Cohort 5. Each cohort consists of three cycles of treatment. Cohort 2 will not be conducted if 700 μ g or 1300 μ g peptide mass is shown to be optimal. Cohorts 7 and 8 will not be conducted if 1300 μ g peptide mass is seen to be too high. Cohorts 3 and 6 require 10 subjects for eight to be completed. All other cohorts are three to five subjects (minimum of three subjects to be completed).

Radioactivity evaluation (Part A)

In Part A, a cumulative radioactivity of 13.5 GBq (4.5 GBq/cycle \times three cycles) with a peptide mass dose of 300 μ g will be evaluated (Table 2).

In Part B, the radioactivity and peptide mass dosing for each cycle in each cohort is illustrated in Table 2.

Radioactivity escalation (Cohorts 1 and 2 – Part B)

Cohort 1 will investigate a radioactivity of 6 GBq/cycle (cumulative radioactivity 18 GBq) with the same peptide mass dose as in Part A (300 μ g) for three cycles (Table 2).

Once the third subject of Cohort 1 has completed at least two cycles, if no safety signal is observed and if the subjects did not reach the cumulative absorbed dose in each of the target

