Although a subject is not obliged to give reason(s) for withdrawing, if a subject is discontinued at any time after entering the study, the investigator should make a reasonable effort to ascertain the reason(s) while fully respecting the subject's rights. The investigator will make every effort to contact the subject and complete the termination status page on the eCRF and, if possible, conduct an EW Visit that will take place 8 weeks after the last administration study medication. In case of discontinuation of treatment/withdrawal from treatment as described in Section 6.4, the EW Visit and the Long-term Follow-up Visits will be performed as planned.

The reasons for treatment and/or study discontinuation should be collected and reported in the eCRF.

Appropriate follow-up of withdrawn subjects will be performed, as required. Attempts to contact subjects who withdraw from a study must be documented.

Withdrawn subjects will be replaced if they do not complete treatment (the first three cycles) due to any reason other than exceedance of organ dose limits, treatment-related safety issues or disease progression.

4.6.2 *Withdrawal Criteria for Optional Biobanking*

Subjects participating to the optional research biobanking program have the right to withdraw their consent at any time and for any reason during the study or during the period of sample storage (i.e. the entire 15 years during which the sample is kept). If a subject wishes to withdraw his consent for biobanking and the samples are still at the investigator site or at Central Laboratory at this time, the investigator must inform the study monitor in writing of the subject's decision and destroy the samples. The study monitor will forward confirmation of the destruction to Biomarker/Biobanking study monitor.

If the samples are at the sponsor's repository (biobanking vendor), the investigator must inform directly Ipsen using the e-mail address, **CCI**, mentioning only the subject study ID in this e-mail. Ipsen will ensure destruction of the samples and all corresponding aliquots and issue confirmation of the withdrawal, which will be forwarded to the investigator. Analyses conducted before the withdrawal will not be affected.

4.6.3 *Study or Site Termination*

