6.4.2 Part B

If any of the following occur, no further ^{177}Lu -OPS201 treatment will be administered:

- subject withdraws his/her consent to further treatment;
- cumulative kidney dose exceeds 23 Gy;
- cumulative bone marrow dose exceeds 1.5 Gy, as determined by image-based dosimetry;
- platelets $<50.0 \times 10^9/\text{L}$ (i.e. Grade 3 or higher);
- if one of the following medical conditions occurs (based on CTCAE v5.0 criteria, see [Appendix 4](#)) and does not resolve within 4 weeks (resolved=toxicity Grade 1 or recovered, and is at the discretion of the investigator):
 - eGFR of $<45 \text{ mL}/\text{min}/1.73\text{m}^2$;
 - liver function tests (total bilirubin, aminotransferases, alkaline phosphatase and gamma glutamyl transferase (GGT) higher than Grade 3 (unless there is treatment-

- related liver toxicity, in which case the study treatment should be stopped or interrupted to enable recovery when deterioration of the liver function is noted);
- any other related AE above Grade 2, except hair loss, lymphopenia, nonfebrile neutropenia lasting <4 weeks.

The investigator can decide at his/her discretion to discontinue the treatment or to reduce the administered radioactivity for further safety reason than those here listed above to prevent a subject from higher grade toxicity.

Before the administration of Cycles 2 and 3 these criteria must be checked. In the event of withdrawal (discontinuation) from treatment only the EW Visit and the long-term follow-up will be performed (with the EW Visit, 8 weeks after the last administration of ¹⁷⁷Lu-OPS201). In some cases, absorbed dose to the bone marrow or kidney may be difficult to evaluate. If there is uncertainty about the radiation dose received to critical organs, but without substantial toxicity, the decision to administer additional cycles is based on continuing to meet requirements of the inclusion criteria, the investigator's judgement and subject's discretion and must be discussed with and agreed by the sponsor. The decision may be either to stop the treatment, administer the full dose or a reduced dose depending on the benefit-risk balance for the subject.

In the situation of persisting Grade 3 and higher bone marrow toxicity, a bone marrow aspirate can be considered, at the discretion of the investigator, if this could contribute to the evaluation of the event.

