- cumulative bone marrow dose exceeds 1.5 Gy, as determined by image-based dosimetry;
- platelets <50.0*10⁹/L (i.e. Grade 3 or higher);
- if one of the following medical conditions occurs (based on CTCAE v5.0 criteria,) and does not resolve within 4 weeks (resolved=toxicity Grade 1 or recovered, and is at the discretion of the investigator):
 - eGFR of <45 mL/min/1.73m²;
 - liver function tests (total bilirubin, aminotransferases, alkaline phosphatase and gamma glutamyl transferase (GGT) higher than Grade 3 (unless there is treatment-related liver toxicity, in which case the study treatment should be stopped or interrupted to enable recovery when deterioration of the liver function is noted);
 - any other related AE above Grade 2, except hair loss, lymphopenia, nonfebrile neutropenia lasting <4 weeks.

The investigator can decide at his/her discretion to discontinue the treatment or to reduce the administered radioactivity for further safety reason than those here listed above to prevent a subject from higher grade toxicity.

Before the administration of Cycles 2 and 3 these criteria must be checked. In the event of withdrawal (discontinuation) from treatment only the EW Visit and the long-term follow-up will be performed (with the EW Visit, 8 weeks after the last administration of ¹⁷⁷Lu-OPS201). In some cases, absorbed dose to the bone marrow or kidney may be difficult to evaluate. If there is uncertainty about the radiation dose received to critical organs, but without substantial toxicity, the decision to administer additional cycles is based on continuing to meet requirements of the inclusion criteria, the investigator's judgement and subject's discretion. The decision may be either to stop the treatment, administer the full dose or a reduced dose depending on the benefit-risk balance for the subject.

In the situation of persisting Grade 3 and higher bone marrow toxicity, a bone marrow aspirate can be considered, at the discretion of the investigator, if this could contribute to the evaluation of the event.

1.3.2 *Efficacy assessments*

The following secondary efficacy variables will be assessed:

- Objective tumour response based on RECIST v1.1 (CT/MRI scan) by calculating BOR, ORR and DCR
- Progression free survival (PFS) based on RECISIT v1.1 (CT/MRI)
- Influence of ¹⁷⁷Lu-OPS201 PRRT on Quality of Life of the Subjects based on change in Quality of Life Questionnaire (QLQ)-C30; GI.NET21) from baseline to EOCT.

CCI

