DRB-B	Cohort 3 First three subjects, EOC-2	Start Cohort 4 with 6 GBq?	If >65% DLTs in Cohort 3 then NO to Cohort 4. If >33% and <67% DLTs in Cohort 3 Cycle 2 then wait for three more subjects in Cohort 3 Cycle 2 and re-evaluate. Otherwise start Cohort 4. Cohort 4 will not start recruiting until Cohorts 1, 3 and 6 are fully recruited
DRB-C	Cohort 4 EOC-1	Start Cohort 5? Continue Cohort 4?	If >33% DLTs in Cohort 4 then NO to Cohort 5. If >33% DLTs in Cohort 4 then STOP. Evaluate peptide mass dosing and lesion receptor saturation. Evaluate next cohort to start and activity dosing.
DRB-D	Cohort 6 EOC-3 All subjects Cohort 4 EOC-1	Start Cohort 7?	If >33% DLT in Cohort 6 Cycle 2 NO to Cohort 7 AND If lesion receptor saturation in Cohort 6 Cycle 2, then no to Cohort 7 AND If >33% DLTs and <67% DLTs in Cohort 4 and receptor modelling suggests Cohort 7 mass dose safer, then start Cohort 7, otherwise no.
DRB-E	Cohort 6 EOC-3 All subjects Cohort 5 EOC-1	Start Cohort 8?	If >33% DLT in Cohort 6 Cycle 2 NO to Cohort 8 AND If lesion receptor saturation in Cohort 6 Cycle 2, then no to Cohort 8 AND If >33% DLTs <67% DLTs in Cohort 5 and receptor modelling suggests Cohort 8 mass dose safer, then start Cohort 8, otherwise no.
DRB-F	Cohort 1 EOC-3 and Cohort 3 EOC-3 and Cohort 5 EOC-1	Start Cohort 2?	If mass dose modelling suggest 300 ug is optimal AND If >33% DLTs in Cohort 1, AND If >33% DLTs in Cohort 5 Start Cohort 2

DLT=dose limiting toxicity; DRB=data review board; EOC=end of cycle; GBq=gigabecquerel.

Note: At each DRB, safety data available from all cohorts will be evaluated to inform decision making.

a although the DRBs are written in alphabetical sequence this is not a chronological order; each one will be conducted when data becomes available which is dependent on subject recruitment. An ad-hoc DRB can be called to ensure continuity of dosing. Although three completed subjects are required for each completed cycle for evaluation, all available subject data in that cohort will be used (e.g. If five subjects are enrolled and all five complete the end of a cycle prior to the DRB, then all five sets of data will be evaluated).

This cumulative activity in the cohort being evaluated will be determined by the following DLT rules:

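### Part B: a low platelet count that permanently ends a subject's dosing is not a DLT if it lasts under 4 weeks, so a cohort can pass the DLT rule at 0/3 with two subjects stopped

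*Protocol*

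**What the plan says.** **DLT definition.** Protocol 3.8 (Part B) counts related AEs of Grade 3 or higher, "with the exception of hair loss, lymphopenia, nonfebrile neutropenia lasting <4 weeks and thrombocytopenia lasting <4 weeks". The synopsis and SAP 3.2.18 define it the same way. The escalation rule is applied to three evaluable subjects. Above 33% DLTs, the next cohort does not open. At or below 33%, with the organ-dose condition met, "the next cohort will be initiated as planned".

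**Stopping rule.** The list in Protocol 6.4.2 opens "If any of the following occur, no further" and goes on to bar treatment. One entry stands alone, worded in SAP 1.3.1.3 as "platelets <50.0*10⁹/L (i.e. Grade 3 or higher"). The four-week recovery clause comes after it and governs a separate sub-list: eGFR, liver tests and "any other related AE above Grade 2, except hair loss, lymphopenia, nonfebrile neutropenia lasting <4 weeks". Thrombocytopenia is not among those exceptions.

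**SAP variant.** SAP 3.2.19 restates the Part B stopping rules differently. It keeps the platelet stop, brings back a neutrophil stop that Protocol 6.4.2 lacks, and adds thrombocytopenia of under 4 weeks to the exceptions in the final bullet.

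**Status of a stopped subject.** In the synopsis and Protocol 3.1.2, a completed subject has had at least three cycles, or "fewer than 3 cycles if one of the following has occurred: exceedance of organ dose limits, treatment-related safety issues or disease progression". Under Protocol 4.6.1, a withdrawn subject is replaced only if the three cycles were not finished "due to any reason other than exceedance of organ dose limits, treatment-related safety issues or disease progression". SAP Table 9, footnote a, says: "Although three completed subjects are required for each completed cycle for evaluation"; it adds that all available data in the cohort are used.

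**The concern.** A DLT count is meant to record toxicity that limits dosing. Here one event limits dosing completely and can still be left out of the count that governs escalation. DLTs are part of the primary safety endpoint (Protocol 3.2.1), and the study is meant to recommend cumulative activity and fractionation for the next phase (Protocol 2.1). A cohort reported as 0/3 would look tolerable at its planned activity even if most of its subjects could not be given that activity.

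The platelet rule also differs from the neutrophil rule. In Part A both counts are stand-alone stops (Protocol 6.4.1). In Part B the protocol dropped the neutrophil stop and exempted short neutropenia, which matches the DLT definition. It made no such change for platelets.

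**Working it through.** **1. The plan's threshold.** SAP 3.2.19 explains >33% of three subjects as more than one of the three to five enrolled. One subject gives 1/3 = 33.3%, 1/4 = 25% or 1/5 = 20%. Two give 2/3 = 66.7%, 2/4 = 50% or 2/5 = 40%. The explanation holds if 33% is read as one third.

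**2. One event through each rule.** Take a related platelet count below 50 ×10⁹/L that lasts under 4 weeks.

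| Rule | Result |
|---|---|
| Protocol 6.4.2; SAP 1.3.1.3; SAP 3.2.19 | Dosing ends |
| Protocol 3.8; SAP 3.2.18 | Not a DLT |
| Synopsis; Protocol 3.1.2 | Subject is completed |
| Protocol 4.6.1 | Subject is not replaced |

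**3. The count.** Two of three subjects have this event and there is no other DLT.
- As written: 0/3 = 0%, so the DLT rule is passed.
- With stops counted: 2/3 = 66.7%, so the next cohort is not initiated. At DRB-B in SAP Table 9, 66.7% meets the >65% row (no Cohort 4). Unrounded, it also meets the row for >33% and <67% (wait for three more subjects), so the two rows overlap.

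**4. Which reviews see a shortened course.** Table 9 reads Cohort 4 (DRB-C, DRB-D) and Cohort 5 (DRB-E, DRB-F) at the end of cycle 1. Every subject has had one cycle by then, so a platelet stop removes no activity from those decisions. Later reviews are affected:
- Cohort 3 is read after cycle 2 (DRB-A, DRB-B). A subject stopped after cycle 1 has had 4.5 of 2 × 4.5 = 9.0 GBq.
- Cohort 1 is read after cycle 3 (DRB-F). A subject stopped after one or two cycles has had 6.0 or 12.0 of 18.0 GBq (33% or 67%).

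For Cohort 1, marrow dose = Gy/GBq × GBq. The protocol quotes 0.077 (Section 1.4) and 0.1 Gy/GBq (Section 1.6), both from other regimens:
- one cycle: 0.077 × 6 = 0.46 to 0.1 × 6 = 0.60 Gy
- two cycles: 0.077 × 12 = 0.92 to 0.1 × 12 = 1.20 Gy
- three cycles: 0.077 × 18 = 1.39 to 0.1 × 18 = 1.80 Gy

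The limit is 1.5 Gy. An early stop keeps a subject below it, while a full course could fall on either side.

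**5. Illustration on assumed rates.** Let s be the chance per subject of a related count below 50, and q the share of such events lasting under 4 weeks. Assume no other DLTs. The documents give neither s nor q. The chance of failing the DLT rule is 3p²(1−p) + p³, with p = s(1−q) as written and p = s if stops count. The difference is the chance that at least two of three are stopped and the rule is still passed. For s = 0.3 and q = 0.5:
- as written, p = 0.15: 3 × 0.0225 × 0.85 + 0.0034 = 0.061, so 93.9% pass
- stops counted, p = 0.30: 3 × 0.09 × 0.70 + 0.027 = 0.216, so 78.4% pass
- difference: 15.5%

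| s | q = 0.25 | q = 0.5 | q = 1 |
|---|---|---|---|
| 0.1 | 1.2% | 2.1% | 2.8% |
| 0.2 | 4.3% | 7.6% | 10.4% |
| 0.3 | 8.7% | 15.5% | 21.6% |
| 0.5 | 18.4% | 34.4% | 50.0% |

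The chance of at least two stops with exactly 0/3 DLTs is smaller unless q = 1. At s = 0.3 it is 1.2%, 5.1% and 21.6% across the same columns.

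**The case against.** **The exemption may be deliberate.** It appears in the same form in the synopsis, Protocol 3.8 and SAP 3.2.18. A subject-level stop that is stricter than the cohort-level DLT is a coherent design. That is fair, but the protocol gives no reason for the difference, and no escalation rule in the available text uses the stops.

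**The Board is not bound by the count.** It reviews every escalation, sees all safety data, and can delay a cohort or extend it to five subjects (Protocol 3.8). Cohorts 2 and 5 open only if no safety signal has been seen (synopsis). This stands, so a reader who infers that escalation would be automatic goes too far. The safety-signal condition is undefined, however, and none of these safeguards says how many platelet stops should hold a cohort. Protocol Appendix 3 and the Board's charter were not available.

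**The stop may not be final.** Protocol 6.2 lets the next cycle start if side effects recover within the 4 weeks, and 6.2.1 lets the sponsor approve a lower activity after recovery from a significant toxicity. Section 6.2.1 points to 6.4 without saying which prevails. This softens the stop in practice but leaves 6.4.2 as written.

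**Evaluable is undefined.** The Table 9 footnote could be read as leaving out subjects who never had the cycle under review, and SAP 3.2.19 ties the step from 6 to 7.4 GBq to the third administration. This is a real ambiguity for later reviews. It does not help at end-of-cycle-1 reviews, where a subject stopped after cycle 1 has had the cycle in question.

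**The information is already tabulated.** SAP 3.2.1.2, 3.2.1.3 and 3.2.1.7 cover TEAEs leading to discontinuation, reduction or delay, Grade 3 and 4 haematology listings, cycles given and cumulative activity. This is correct, and it makes a further table unnecessary. None of it enters the escalation rule.

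**Conclusion.** The inconsistency is in the text and should be fixed. With two of three subjects permanently stopped for short, related platelet events, the written count is 0/3 against 2/3 = 66.7% if the stops counted, and the DLT rule gives opposite answers. This assumes that both events last under 4 weeks, that there is no other DLT, that completed subjects are taken as evaluable, and that the organ-dose condition is met. Whether the cohort then escalates is the Board's decision.

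Three stronger inferences are not supported:
- **That a platelet stop lowers the activity or marrow dose judged at the Cohort 4 and 5 reviews.** Those are read at the end of cycle 1. The shortened course matters only for reviews after cycle 2 or 3 and for the final dose recommendation.
- **That the rate of short events is about 25%, from the pilot's one case in four patients (Protocol 1.3.6).** That patient recovered within 8 weeks of injection, but the duration is not stated. The event may have lasted 4 weeks or more and so have met the DLT definition. The exact 95% interval for 1/4 is 0.6% to 80.6% in any case. The percentages above show sensitivity to assumptions and are not estimates.
- **That the severe thrombocytopenia in the investigator-sponsored study (Protocol 1.4) would be missed.** Those events were long-lasting and would be DLTs.

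**What to change.** In Protocol 3.8 and SAP 3.2.18 and 3.2.19, state that a related Grade 3 or higher thrombocytopenia that leads to permanent discontinuation under Protocol 6.4.2 is a DLT whatever its duration. Make the same edit in the synopsis. This also settles the status of an event still open at a review once it has ended the subject's dosing.

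Reconcile the Part B stopping list in SAP 3.2.19 with Protocol 6.4.2 on the neutrophil stop and on the exemption of short thrombocytopenia.

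Do not deal with the problem by removing toxicity-stopped subjects from the evaluable set. That would bias the DLT rate towards subjects who tolerate treatment.

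The cost is a one-sentence protocol amendment with matching SAP text. No new data are needed: platelet counts, cycles, administered activity and reasons for stopping are already collected. Some cohorts that would now proceed would be held or extended. The Part B definition would also differ from Part A, which has the same mismatch between 6.4.1 and 3.8, unless Part A DLTs are re-tabulated under the new definition.
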